4.2. Exclusion Criteria

Any potential subject who meets any of the following criteria will be excluded from participating in the study.

1. Subject has known allergies, hypersensitivity, or intolerance to imetelstat or its excipients (refer to the IB²⁵);
2. Criterion 2 modified per Amendment 5.
 - 2.1 Subject has received an experimental or investigational drug or used an invasive investigational medical device within 30 days prior to C1D1 (Part 1) or Randomization (Part 2) (defined in Section 3.1) or is currently enrolled in an investigational study;
3. Prior treatment with imetelstat;
4. Criterion modified per Amendment 2.
 - 4.1 Have received corticosteroids >30 mg/day prednisone or equivalent; or growth factor treatment within 4 weeks prior to C1D1 (Part 1) or Randomization (Part 2);

-
5. Criterion modified per Amendment 2.
 - 5.1 Prior treatment with a hypomethylating agent (eg, azacitidine, decitabine);
 - 5.2 Criterion 5.2 replaced by criterion 5.2.1 per Amendment 5.
 - 5.2.1 Prior treatment with lenalidomide, thalidomide, or other thalidomide analogues;
 - 5.3 Criterion 5.3 replaced by criterion 5.3.1 per Amendment 5.
 - 5.3.1 Has received an ESA or any anti-MDS therapy, chemotherapy, immunomodulatory, or immunosuppressive therapy within 4 weeks prior to C1D1 (Part 1) or Randomization (Part 2) (8 weeks for long-acting ESAs);
 6. Prior history of hematopoietic stem cell transplant;
 7. Anemia attributed to factors other than MDS (including hemolysis, chronic renal failure, hepatitis, gastrointestinal bleeding);
 8. Major surgery within 4 weeks prior to C1D1 (Part 1) or Randomization (Part 2) (excluding the placement of vascular access and other minor surgical procedures);
 9. Diagnosed or treated for malignancy other than MDS, except:
 - 9.1. Malignancy treated with curative intent and with no known active disease present for ≥ 3 years before C1D1 (Part 1) or Randomization (Part 2)
 - 9.2. Adequately treated non-melanoma skin cancer or lentigo maligna without evidence of disease
 - 9.3. Adequately treated cervical carcinoma in situ without evidence of disease;
 10. Clinically significant cardiovascular disease such as uncontrolled or symptomatic arrhythmias, congestive heart failure, or myocardial infarction within 6 months of C1D1 (Part 1) or Randomization (Part 2), or any Class 3 (moderate) or Class 4 (severe) cardiac disease as defined by the New York Heart Association Functional Classification;
 11. Known history of human immunodeficiency virus (HIV) or any uncontrolled active systemic infection requiring IV antibiotics;
 12. Criterion modified per Amendment 1.
 - 12.1. Active systemic hepatitis infection requiring treatment (carriers of hepatitis virus are permitted to enter the study), or known acute or chronic liver disease including cirrhosis;
 13. Females who are pregnant or are currently breastfeeding or planning to become pregnant while enrolled in this study or within 1 month after the end of dosing;
 14. Subject is a man who plans to father a child while enrolled in this study or within 3 months after the end of dosing;
 15. Any life-threatening illness, medical condition, or organ system dysfunction which, in the investigator's opinion, could compromise the subject's safety, interfere with the imetelstat metabolism, or put the study outcomes at undue risk; Subject has any condition for which, in the opinion of the investigator, participation would not be in the best interest of the subject (eg, compromise the well-being) or that could prevent, limit, or confound the protocol-specified assessments;
-

16. Subject was previously assessed as having IPSS intermediate-2 or high risk MDS;
17. Subject with del(5q) karyotype;
18. Subject with MDS/myeloproliferative neoplasm Overlap Syndrome.

4.3. Prohibitions and Restrictions

Potential subjects must be willing and able to adhere to the following prohibitions and restrictions during the course of the study to be eligible for participation:

1. A woman of childbearing potential must remain on a highly effective method of birth control (see inclusion criteria) during the study. For females, these restrictions apply for 1 month after the end of dosing.
2. A man who is sexually active with a woman of childbearing potential must use an adequate method of birth control and all men must also not donate sperm during the study. For males, these restrictions apply for 3 months after the end of dosing.
3. Section 8 details prestudy and concomitant therapies used in this study.

5. TREATMENT ALLOCATION AND BLINDING

5.1. Treatment Allocation

Part 1: Randomization will not be used in Part 1; all subjects will receive imetelstat. As Part 1 is an open-label design, blinding procedures are not applicable.

Part 2: Subjects will be randomly assigned 2:1 in Part 2 to receive either imetelstat or placebo. Randomization will be based on a computer-generated randomization schedule prepared before the study by or under the supervision of the sponsor. Randomization will be stratified by prior RBC transfusion burden (≤ 6 or > 6 units RBC) and by IPSS risk group (low versus intermediate-1). Prior RBC transfusion burden is defined as the maximum number of RBC units transfused over an 8-week period during the 16 weeks prior to Randomization. Pre-transfusion Hb should be ≤ 9.0 g/dL to count towards the 4 units total unless there is clinical rationale for transfusing at a higher Hb level. The interactive web response system (IWRS) will assign a unique treatment code, which will dictate the treatment assignment for the subject. The requestor must use his or her own user identification and personal identification number when contacting the IWRS and will then give the relevant subject details to uniquely identify the subject.

5.2. Blinding and Unblinding

The investigator will not be provided with randomization codes. The codes will be maintained within the IWRS, which has the functionality to allow the investigator to break the blind for an individual subject.

Data that may potentially unblind the treatment assignment (ie, study drug plasma concentrations) will be handled with special care to ensure that the integrity of the blind is maintained and the potential for bias is minimized. This may include making special provisions, such as segregating

the data in question from view by the investigators, clinical team, or others as appropriate until the time of database lock and unblinding.

Under normal circumstances, the blind should not be broken until all subjects have completed the study and the database is finalized. Otherwise, the blind should be broken only if specific emergency treatment/course of action would be dictated by knowing the treatment status of the subject. In such cases, the investigator may in an emergency determine the identity of the treatment by contacting the IWRS. It is recommended that the investigator contact the sponsor or its designee if possible, to discuss the particular situation, before breaking the blind. Telephone contact with the sponsor or its designee will be available 24 hours per day, 7 days per week. In the event the blind is broken, the sponsor must be informed as soon as possible. The date, time, and reason for the unblinding must be documented by the IWRS, in the appropriate section of the case report form (CRF), and in the source document. The documentation received from the IWRS indicating the code break must be retained with the subject's source documents in a secure manner. Subjects who have had their treatment assignment unblinded should continue to return for scheduled evaluations and with sponsor approval may continue study drug. It is the intent that all subjects, investigators, and study team members, except some required project roles (eg, members associated with DMC and HEC), will remain blinded to treatment group assignment at least until the primary efficacy analysis (12 months after the last subject is randomized in the main study of Part 2). As of Protocol Amendment 8, subjects, investigators, and study team members will be unblinded after primary efficacy analysis.

For subjects participating in the Ventricular Repolarization substudy (Part 2) after Protocol Amendment 7, additional information for unblinding is provided in Attachment 11.

6. DOSAGE AND ADMINISTRATION

The term 'Study Drug' refers to treatment with either imetelstat or placebo.

Subjects may receive study drug until disease progression, unacceptable toxicity, or withdrawal of consent.

Supportive Care

All subjects will receive supportive care (including transfusions or myeloid growth factors) as needed per investigator discretion and according to local standard practices. Should an exceptional situation arise where it is deemed clinically necessary to give a transfusion for a Hb >11 g/dL, the reasons should be documented in the CRF.

Study Drug (Imetelstat or Placebo)

Imetelstat Sodium (GRN163L) for injection (imetelstat) is the investigational product in this study and will be provided by the sponsor.

Placebo will be supplied by the sponsor.

Study drug will be administered as a 2-hour IV infusion (\pm 10 minutes) at a constant rate using an infusion pump.

The baseline weight (ie, body weight determined at Screening) will be used to calculate the dose of study drug to the nearest 0.1 mg. The dose should be recalculated if there is a \geq 10% weight change from baseline. Note that the total dose may be recalculated more frequently (eg, at each study visit) depending on local practice. Study drug will be administered IV on a 28-day cycle.

The first dose of study drug should be administered within 72 hours of enrollment (Part 1) or randomization (Part 2) in IWRS.

All subjects in Parts 1 and 2 will receive a starting dose of 7.5 mg/kg of study drug given IV every 4 weeks. Subjects whose dose was previously escalated (before Amendment 2) may continue at the 9.4 mg/kg dose. Study drug dose delay or reduction for Grade 3 or Grade 4 toxicity will be instituted as needed, per the instructions provided in Table 7, Table 8, Table 9, Table 10, and Table 11. Note that these instructions are intended for Grade 3 or Grade 4 toxicities observed at the time of the planned dose on Day 1 of the next cycle. These instructions are not applicable when toxicities occur mid-cycle and subsequently resolve to Grade $<$ 3 by the time of the next planned dose.

The study drug may be held for up to 28 days from the expected start date of the scheduled cycle; a hold $>$ 28 days must be reviewed and approved by the sponsor. The study drug should be discontinued permanently if it cannot be restarted within 28 days due to toxicity. If the subject is exhibiting an otherwise positive clinical response to treatment and the toxicity appears to be manageable, contact the sponsor to discuss the specific case before study drug is discontinued.

Treatment During the Extension Phase

Dose modification guidelines provided in the following sections will continue in the Extension Phase. Subjects may receive treatment in the Extension Phase until there is loss of benefit or unacceptable toxicity, as determined by the investigator according to local standard of care.

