Subjects enrolled in Part 1 will continue through the Part 1 treatment and posttreatment follow-up phases after initiation of Part 2. Subjects enrolled in Part 1 of the study are not eligible to enroll in Part 2.

For Part 2, an additional 45 evaluable subjects will be enrolled in a separate substudy investigating the effects of imetelstat exposure on ventricular repolarization. Details regarding the Ventricular Repolarization substudy, including eligibility criteria and study procedures (including Time and Events Table) for participating subjects are provided in Attachment 11.

The term 'Study Drug', as used in this protocol, refers to either imetelstat or placebo in Part 2. Each treatment cycle will consist of 4 weeks (28 days). All subjects receiving study drug must be premedicated to prevent infusion reactions (see Section 6.2). The starting dose of the study drug is 7.5 mg/kg every 4 weeks. In Part 1 of the study, subjects whose dose was previously escalated (before Amendment 2) may continue at the 9.4 mg/kg dose. Study drug dose delay or reduction

for Grade 3 or Grade 4 toxicities will be instituted as per the instructions provided in Table 7, Table 8, Table 9, and Table 10.

Supportive care, including transfusions or myeloid growth factors, is to be administered to all subjects as needed per investigator discretion and according to local standard practices.

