6.1.3. Dose Modifications for Liver Function Test Elevations and Hepatic Adverse Events

The actions in Table 10 should be taken for Grade 3 or 4 LFT elevations (AST, ALT and bilirubin), Grade 3 or 4 hepatic adverse events, and Grade ≥ 2 AST or ALT with Grade ≥ 2 bilirubin present at the planned start of a dosing cycle.

Table 10: Dose Modifications for Liver Function Test Elevations and Hepatic Adverse Events

Adverse Event	Action to be taken
Grade 3 or 4 AST, ALT, or bilirubin For ALT or AST $>8 \times ULN$ or baseline, contact sponsor and consider discontinuing drug altogether	
 • HOLD study drug and report as adverse event of interest (AEI) • Determine relatedness to study drug (i.e. extensive investigation^a to determine an alternative likely cause(s) for the event) 
 ○ If considered at least possibly related, after recovery to baseline, restart study drug at one dose level lower. ○ If not related, after recovery to baseline, restart study drug without dose reduction. • If the event recurs and is related, study drug should be discontinued

Adverse Event	Action to be taken
Grade 3 or 4 hepatic adverse event	
 • HOLD study drug and report as AEI • Determine relatedness to study drug (i.e. extensive investigation^a to determine an alternative likely cause(s) for the event) 
 ○ If considered at least possibly related, after recovery to baseline, restart study drug at one dose level lower. ○ If not related, after recovery to baseline, restart study drug without dose reduction. • If the event recurs and is related, study drug should be discontinued
Grade \geq 2 AST or ALT with concomitant Grade \geq 2 bilirubin* *Subjects with Grade 2 bilirubin at study entry should have worsening bilirubin with concomitant Grade 2 AST or ALT elevation	
 • HOLD study drug and report as AEI • Determine relatedness to study drug (i.e. extensive investigation^a to determine an alternative likely cause(s) for the event) 
 ○ If considered at least possibly related, discontinue study drug ○ If not related, after recovery to baseline, study drug can be restarted at same dose 
 ▪ If upon rechallenge the event recurs, study drug should be discontinued

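### Sections 6 and 3.1 and Table 10 of the protocol do not agree on whether study drug is held for combined Grade 2 AST/ALT and bilirubin elevation on Day 1

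*Protocol*

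**What the plan says.** **Section 6 (Dosage and Administration).** Dose delay or reduction for Grade 3 or 4 toxicity is to follow five tables: "per the instructions provided in Table 7, Table 8, Table 9, Table 10, and Table 11". Two sentences then limit them. The first sets the grade and the day, meaning the day the following cycle is due: "Note that these instructions are intended for Grade 3 or Grade 4 toxicities observed at the time of the planned dose on Day 1". The second is an exemption: "These instructions are not applicable when toxicities occur mid-cycle and subsequently resolve to Grade $<$ 3 by the time of the next planned dose". Neither sentence makes an exception for liver events.

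**Section 3.1 (Overview of Study Design).** The same grade scope is given for changes to dosing, again naming Table 10: "for Grade 3 or Grade 4 toxicities will be instituted as per the instructions provided in Table 7, Table 8, Table 9, and Table 10".

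**Section 6.1.3 and Table 10.** The triggers go below Grade 3. Besides Grade 3 or 4 liver test elevations, two more are listed, both tied to the day a cycle is due: "Grade 3 or 4 hepatic adverse events, and Grade ≥ 2 AST or ALT with Grade ≥ 2 bilirubin present at the planned start of". The third row of Table 10 carries the combined trigger. Its actions are to hold, report as an adverse event of interest and investigate, then to discontinue if the event is at least possibly related. If it is unrelated, the same dose may be restarted after recovery to baseline. The row's footnote confirms that Grade 2 values are meant: "Subjects with Grade 2 bilirubin at study entry should have worsening bilirubin with concomitant Grade 2 AST or ALT elevation".

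**Section 9.1.4 (Treatment Phase).** Dose modifications are to follow the criteria in 6.1.1, 6.1.2 and 6.1.3. Nothing is said about how those sections rank against the note in Section 6.

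**The concern.** A site deciding on Day 1 whether to infuse can find two answers for the same liver results. Section 6 can be read as saying that Table 10 does not apply, while Table 10 says to hold.

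The row affected is a strict one. In the other two rows of Table 10, a first related event leads to a restart one dose level lower after recovery, although the first row also asks sites to consider discontinuation above a stated ALT/AST limit. The combined row is the only one in that table where a first related event requires discontinuation. For such an event the two readings are infusion at the current dose, or a hold followed by permanent discontinuation.

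Section 1.1.5.2.3 describes liver test abnormalities and hepatic events as the adverse events of concern so far. Sections 6 and 9.1.6 carry the dose-modification rules into the Extension Phase, so the conflict continues there.

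**Working it through.** No sample size, power or error rate is involved. The check compares the trigger conditions case by case.

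**Inputs**
- Scope and exemption: Section 6. The scope is repeated in Section 3.1.
- Combined trigger and actions: Section 6.1.3 and the third row of Table 10.
- Grade limits as printed in Section 9.8: ALT or AST is Grade 2 or higher above 3.0 x ULN and Grade 3 or higher above 5.0 x ULN. Bilirubin is Grade 2 or higher above 2.0 x ULN and Grade 3 or higher above 3.0 x ULN.
- By subtraction, Grade 2 is above 3 and up to 5 x ULN for ALT/AST, and above 2 and up to 3 x ULN for bilirubin.

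**Cases on Day 1** (illustrative values; bilirubin normal at entry, so the Table 10 footnote does not come into play)

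| Case | Section 6 | Section 6.1.3 and Table 10 | Result |
|---|---|---|---|
| 1. Grade 3 or 4 AST, ALT or bilirubin present | Tables apply | Hold | Agree |
| 2. Mid-cycle ALT 6x and bilirubin 3.5x ULN (both Grade 3), now 4x and 2.5x (both Grade 2) | Exempted by the second sentence | Hold; discontinue if related | Direct conflict |
| 3. ALT 4x and bilirubin 2.5x ULN, never higher | Outside the scope in the first sentence | Hold; discontinue if related | Scope mismatch |
| 4. Mid-cycle Grade 3 ALT alone, now Grade 2, with bilirubin below Grade 2 | Exempted | No row triggered | Agree |

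Within Table 10 the disagreement is therefore confined to Day 1 results in which both components are Grade 2. That is the whole range the combined row adds to the Grade 3/4 row. Case 2 rests on the exemption sentence and case 3 on the sentence before it, so both need attention.

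**Table 11.** Section 6 also places Table 11 under the Grade 3/4, Day 1 scope, yet Table 11 gives actions for Grade 1 and Grade 2 infusion reactions while the infusion is running. Section 3.1 stops at Table 10.

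**Frequency.** Section 1.1.5.2.3 reports, for the nine MDS subjects of Study CP14B019, Grade 1 or 2 abnormalities in 67% for ALT, 67% for AST and 11% for total bilirubin, with no Grade 3 or 4 abnormality. In counts:
- 0.67 x 9 = 6.03, about 6 subjects each for ALT and AST.
- 0.11 x 9 = 0.99, about 1 subject for bilirubin.

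At most one of the nine can have had the combined pattern. Grades 1 and 2 are pooled and joint occurrence is not reported, so this is a ceiling for a very small cohort and not an estimate for Part 2.

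**The case against.** The best case against the point is that the protocol can be read as consistent.

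- Section 9.1.4 sends the reader to 6.1.3, which states the combined trigger in terms.
- Section 6 says what its instructions are intended for. The current text does not contain the word *only*, so it can be taken as silent on a Grade 2 plus Grade 2 event, with 6.1.3 supplying the rule.
- A fully literal reading would also switch off the Table 11 actions for Grade 2 infusion reactions, which suggests that the note was meant to limit the Grade 3/4 rules.
- Even in case 2, one could say that the Grade 3/4 row has lapsed and the combined row applies to what is present on Day 1.

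Much of this stands for case 3, which is why it is called a scope mismatch and not a contradiction. It does not dispose of case 2. Section 6 names Table 10 and says when its instructions do not apply, and no text ranks 6.1.3 above that sentence. The dosing rows of Tables 3 and 5 refer sites to Section 6, which contains both the note and 6.1.3, so they do not settle it either.

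Other safeguards hold on any reading. The combined pattern is an adverse event of interest under Sections 9.8 and 12.3.3.1, laboratory results must be reviewed before dosing (9.1.4), and the Hepatic Expert Committee reviews all hepatic events and liver test abnormalities (11.12).

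A reader might infer that Section 6 disables the Table 10 hold. The documents do not support that, because 6.1.3 and Table 10 still state it. Nor do they show a biased hepatic comparison between arms: Part 2 is double-blind and the same text applies to both groups.

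**Conclusion.** The inconsistency is in the current text and does not depend on the amendment history. It is a direct conflict for a mid-cycle Grade 3 event that is Grade 2 plus Grade 2 on Day 1. It is a scope mismatch for a combined Grade 2 elevation that was never higher. By the limits in Section 9.8, the range is ALT or AST above 3 and up to 5 x ULN with bilirubin above 2 and up to 3 x ULN. It affects hold and discontinuation, not reporting. Table 11 has a similar mismatch of scope.

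The number of subjects affected is unknown. The 67% for a single transaminase should not be read as the frequency of the combined event, since bilirubin was abnormal in only 11% of the same cohort. The conclusion assumes that the grade limits in Section 9.8 are those used for Table 10, and that no site instruction outside these documents already settles the order of precedence. No view is taken on which clinical rule is right.

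**What to change.** Reconcile Sections 3.1, 6 and 6.1.3 with Table 10, and Section 6.2 for Table 11. Section 6 should state its grade scope and its exemption for mid-cycle toxicities that have eased table by table, and should agree with 6.1.3 on combined AST/ALT and bilirubin events. The sponsor, with the Hepatic Expert Committee, decides which rule governs a combined event that is Grade 2 on Day 1. The agreed wording should then be the same wherever the rule appears.

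The cost is wording changes in Sections 3.1 and 6 and a memo to sites. No new assessments are needed, because laboratory results are already reviewed before each dose.

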6.1.1. Dose Modifications for Hematologic Toxicities

For any occurrence of Grade ≥ 3 thrombocytopenia or neutropenia, additional weekly blood counts should be performed until there is a return to baseline values. For treatment of hematologic toxicities, granulocyte-colony stimulating factors (G-CSF) are permitted for neutropenia as well as blood transfusions for anemia or thrombocytopenia.

The actions in Table 7 should be taken for Grade 3 hematologic toxicities present at the planned start of a dosing cycle. The actions in Table 8 should be taken for imetelstat-related Grade 4 hematologic toxicities at the planned start of a dosing cycle. It is recommended to contact the sponsor before discontinuing treatment due to Grade 3 or Grade 4 hematologic toxicity, particularly when the hematologic toxicity is without clinical consequences. Note that for Grade 3 or Grade 4 hematologic toxicities that are not considered related to imetelstat, the dose should still be held until recovery to ANC $1 \times 10^9/L$ and platelets $50 \times 10^9/L$.

Table 7: Dose Modifications for Grade 3 Hematologic Toxicities

Occurrence	Action
First	Hold study drug until recovery to ANC $1.0 \times 10^9/L$ and platelets $50 \times 10^9/L^*$; may restart at most recent dose level
Second	Hold study drug until recovery to ANC $1.0 \times 10^9/L$ and platelets $50 \times 10^9/L^*$; restart at 1 dose level lower
Third	Hold study drug until recovery to ANC $1.0 \times 10^9/L$ and platelets $50 \times 10^9/L^*$; restart at 1 dose level lower
Fourth	Discontinue study drug**

*For any other hematologic toxicities, the minimum counts for restarting should be at the Investigator's discretion

** Contact the sponsor to discuss the specific case before study drug is discontinued for hematologic toxicity

Table 8: Dose Modifications for Grade 4 Hematologic Toxicities

Occurrence	Action
First	Hold study drug until recovery to ANC $1.0 \times 10^9/L$ and platelets $50 \times 10^9/L^*$; restart at 1 dose level lower
Second	Hold study drug until recovery to ANC $1.0 \times 10^9/L$ and platelets $50 \times 10^9/L^*$; restart at 1 dose level lower
Third	Discontinue study drug**

*For any other hematologic toxicities, the minimum counts for restarting should be at the Investigator's discretion

** Contact the sponsor to discuss the specific case before study drug is discontinued for hematologic toxicity

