6.1.2. Dose Modifications for Non-hematologic Toxicities, Excluding Hepatic Toxicities

The actions in Table 9 should be taken for Grade 3 or 4 non-hematologic/non-hepatic toxicities present at the planned start of a dosing cycle. For nausea and vomiting, only Grade 3 or 4 events which persist despite optimal antiemetic therapy should be considered for dose modification.

Table 9: Dose Modifications for Grade 3 and 4 Non-hematologic/Non-hepatic Toxicities

Occurrence	Action
First	Hold study drug until recovery to Grade ≤ 1 or baseline; restart at 1 dose level lower
Second	Hold study drug until recovery to Grade ≤ 1 or baseline; restart at 1 dose level lower
Third	Discontinue study drug

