6.2. Infusion-Related Reactions

All subjects receiving an infusion of study drug must be premedicated with an antihistamine (diphenhydramine 25 to 50 mg or equivalent) and a corticosteroid (hydrocortisone 100 to 200 mg or equivalent), either intravenously or orally. Premedications may be administered per local standard of care approximately 1 hour prior to study drug infusion. If per Investigator's discretion premedication(s) is/are contraindicated for a subject, modifications should be reviewed and approved by the sponsor's Medical Monitor. It is recommended that subjects are monitored for at least 1 hour after the infusion has been completed.

Subjects should be carefully observed during study drug infusions. Trained study staff at the clinic should be prepared to intervene in case of any infusion reactions. If an infusion-related reaction develops, then the infusion should be temporarily interrupted and the actions in Table 11 should be taken. If possible, an unscheduled blood sample to determine antibodies to imetelstat (immunogenicity) should be drawn as soon as possible after the infusion-related reaction for potential immune response analysis.

Table 11: Management of Infusion-Related Reactions

Severity [per CTCAE 4.03]	Recommended action
Grade 1 [Mild transient reaction; infusion interruption not indicated; intervention not indicated]	
 • Evaluate and manage symptomatically as needed • May complete infusion if reaction remains mild, with stable vital signs and does not worsen to Grade 2
Grade 2 [Therapy or infusion interruption indicated but responds promptly to symptomatic treatment (eg, antihistamines, NSAIDs, narcotics, IV fluids); prophylactic medications indicated for <=24 hrs]	
 • Stop infusion • Manage symptomatically as needed • After recovery to Grade \leq1, resume infusion at half the previous rate for 30 minutes 
 – If no further symptoms occur, complete the infusion at the full dose rate – If the intensity of the adverse event returns to Grade 2 after restart of the infusion, then the procedure described in this section may be repeated at the investigator's discretion. Should the intensity of the adverse event increase to Grade 2 for a third time, discontinue imetelstat for that cycle.

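### Section 6 wrongly places the infusion-reaction table (Table 11) under a rule meant for toxicity still present at the next dose: a minor cross-reference error in a safety rule

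*Protocol*

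**What the plan says.** Protocol Section 6, under the study drug heading, says that delay or reduction of the dose for Grade 3 or 4 toxicity is done "per the instructions provided in Table 7, Table 8, Table 9, Table 10, and Table 11". The next sentence says these instructions are meant for Grade 3 or 4 toxicity observed when the Day 1 dose of the next cycle is due. The one after that adds an exemption: "These instructions are not applicable when toxicities occur mid-cycle and subsequently resolve to Grade", completed by a threshold of below 3 by the time of the next planned dose.

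Table 11 is the infusion-reaction table and belongs to Section 6.2, which says: "If an infusion-related reaction develops, then the infusion should be temporarily interrupted and the actions in Table 11 should be taken". Its Grade 3 row allows a restart once the event resolves or falls to Grade 1, and calls for discontinuation if Grade 3 is reached a third time. Its Grade 4 row calls for the infusion to be stopped, supportive care and discontinuation. Neither row makes an exception for a reaction that later resolves.

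**The concern.** The Section 6 limit makes sense for blood counts, liver tests and similar toxicities, where the question is whether the subject is fit for the next dose. It does not suit an acute infusion reaction, which will usually be over long before the next 28-day cycle. With Table 11 on the list, Section 6 read word for word switches off the discontinuation in the very situation it was written for. A site relying on Section 6 could argue for another cycle after a resolved life-threatening reaction, while a site following Section 6.2 and Table 11 would stop.

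The wording is still in use. Section 9.1.6 and Table 5 send sites back to Section 6 for dose modification in the Extension Phase.

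**Working it through.** No arithmetic applies beyond counting, and the plan states no figure to reproduce. The check sets the texts side by side.

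**Step 1. Does each table's own section repeat the Day 1 condition?**

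| Table | Section | Local wording | Repeated? |
|---|---|---|---|
| 7 | 6.1.1 | "The actions in Table 7 should be taken for Grade 3 hematologic toxicities present at the planned start of a dosing cycle" | Yes |
| 8 | 6.1.1 | "The actions in Table 8 should be taken for imetelstat-related Grade 4 hematologic toxicities at the planned start of a dosing cycle" | Yes |
| 9 | 6.1.2 | "non-hematologic/non-hepatic toxicities present at the planned start of a dosing cycle" | Yes |
| 10 | 6.1.3 | "bilirubin present at the planned start of a dosing cycle" | Yes |
| 11 | 6.2 | Actions taken when a reaction develops | No |

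The condition is repeated for 4 of the 5 listed tables. Table 11 is the exception.

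**Step 2. Compare the parallel sentence.** Section 3.1 makes the same statement about delay or reduction for Grade 3 or 4 toxicity, but "as per the instructions provided in Table 7, Table 8, Table 9, and Table 10". Table 11 is not there.

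**Step 3. Which rows of Table 11 are affected?** Grade 1 has no stop. The third-time Grade 2 stop is for that cycle only. Grade 3 (third time) and Grade 4 carry a discontinuation without a cycle limit. That is 2 of 4 rows.

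**Step 4. Apply Section 6 literally.** Take a Grade 4 reaction during the Day 1 infusion of one cycle that has resolved when the next Day 1 dose is due. It is not a Grade 3 or 4 toxicity observed at that next dose, so it falls outside the sentence on what the instructions are intended for. That sentence does not depend on the term mid-cycle. The exemption sentence points the same way if a Day 1 infusion reaction counts as mid-cycle, which the text does not settle. Section 6.2 and Table 11 say to discontinue the same subject. The two sections give different answers, and I found no rule on which prevails.

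**Step 5. What is not in doubt.** The immediate steps (stopping the infusion and giving supportive care) are unaffected. Only the discontinuation that carries into later cycles is open to dispute.

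**The case against.** The case for reading the protocol safely as it stands is strong.

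- The Section 6 sentence opens by speaking of delaying or reducing the dose, and Table 11 contains neither a next-cycle delay nor a dose-level reduction. This makes the safe reading more likely. It is not conclusive, because Tables 7 to 10 also contain discontinuation steps and are governed by the same sentence.
- The literal reading would empty Table 11. The table includes Grade 1 and 2 reactions and works during the infusion, and its Grade 3 row presupposes resolution before a restart. This is good evidence of intent, but it shows that the cross-reference is wrong; it does not remove it.
- A reaction on Day 1 is arguably not mid-cycle. That is fair, but it answers only the exemption sentence.
- The Amendment 1 summary of changes attributes the Day 1 clarification to Sections 6 and 6.1.1 to 6.1.3, and not to 6.2. It also gives a table range that then included the infusion-reaction table. This suggests an old slip and that infusion reactions were not the target. It describes superseded text, so it bears on intent only.
- Table 11 heads its column as recommended actions, so it is less rigid than a mandatory rule. Section 6 itself ends treatment at unacceptable toxicity, and Section 10.2 lets the investigator stop for safety.

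A reader might also infer that Section 6.2 contradicts the Grade 1 row, since it interrupts the infusion for any reaction while that row describes interruption as not indicated. The documents do not support this. That phrase sits in the bracketed grade definition, not in the action column, and a brief pause followed by completion satisfies both texts.

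**Conclusion.** Section 6 is wrong as literally written on one cross-reference, and the error touches an operative safety rule. It is minor. The likely practice is the safe one: Section 6.2 is the more specific section, its instruction carries no timing condition, and Section 10.2 stands behind it.

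A reader might infer that subjects are left unprotected after a severe infusion reaction, or that sites will re-dose them. The documents do not support either inference. What they show is a stopping rule that can be disputed when it should have a single reading.

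The scope is one of five listed tables and two of the four rows in Table 11. No frequency can be attached, because the documents give no count of Grade 4 or third-time Grade 3 infusion reactions. The conclusion that Table 11 was listed unintentionally rests on Section 3.1 and on the local wording of Sections 6.1.1 to 6.2. Nothing here affects type I error, power, sample size or the primary endpoint.

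**What to change.** In Section 6, end the list of tables at Table 10, as Section 3.1 does. After the exemption sentence add: *Infusion-related reactions are managed under Section 6.2 and Table 11 when they occur; a discontinuation required by Table 11 applies even if the reaction resolves before the next planned dose.*

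The added sentence is worth having as well as the deletion, because the Grade 3 and 4 rows, unlike the Grade 2 row, do not say how long the discontinuation lasts.

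The cost is one deletion and one sentence at the next amendment. Section 6.2 and Table 11 stay as they are, and no data, visits or analyses change.
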